1.1 Title

The *PREHAB* Study - Pre-operative Rehabilitation for reduction of Hospitalization After coronary Bypass and valvular surgery.

1.3 Coordinating Centre

The St. Boniface Hospital/I.H. Asper Clinical Research Institute will be the coordinating centre and data custodians for this national study. All data management and analysis will be conducted at the St. Boniface Hospital.

2 Background and Rationale for Project

2.1 Introduction

Growing burdens of heart disease in an aging population has resulted in cardiac surgery being offered to older and increasingly frail patients with multiple co-morbidities. Newer minimally invasive procedures are now being performed in very frail octo- and nonagenarian patients previously deemed inoperable. By 2031, 25% of Canadians will be older than 65 years and by extension, greater numbers of frail elderly will be offered cardiac surgery. As such, it has become critically important for the health care system to develop strategies to improve clinical outcomes and provide patient and caregiver support. In Canada, when a patient requires elective cardiac surgery, they are placed on a “waiting list” for as long as 3-4 months. While this waiting system is safe and very few patients die while waiting for heart surgery, we (see *3.1.1 Preliminary Data Informing Study Methodology*) and others have identified that patients on surgical waitlists engage in very little physical activity as they wait “in fear, and feel powerless”. This can be problematic for the already deconditioned frail, elderly patient as at present, there is no formal process for engaging frail elderly patients during this wait period.

2.2 Exercise Rehabilitation

Cardiovascular rehabilitation has been proven to decrease morbidity and mortality in patients with established and unrepairs cardiac disease(4)(5)(6)(7)(8), and to be safe in patients who are elderly,(9)(10)(11)(12)(13) and have heart failure (7)(14)(15)(16) in both hospital and community-based programs. (6)(17)(18) The proposed *Prehab* intervention has been designed with consultation with the 4 cardiac rehabilitation program sites involved in the project and according to the evidence-based best-practice guidelines published by the Canadian Association of Cardiac Rehabilitation(19), the recently published Canadian Cardiovascular Society Quality Indicators for cardiac rehabilitation(20) and the ACSM guidelines for exercise prescription in patients with cardiovascular disease (see <http://www.acsm.org/docs/current-comments/exercise-for-persons-with-cardiovascular-disease.pdf>). (21) All patients, in both aspects of the study, are automatically referred to participate in a postoperative CR program, of their own accord, after their cardiac surgery as part of current standard of care.

2.3 Identification of Potential Opportunity

This wait period, therefore, presents a significant opportunity to optimize preoperative risk factors in these vulnerable patients. The *Prehab* study (an interdisciplinary model of care to maximize the physical, nutrition, psychological reserve and cardiac risk profile of “frail” elderly patients undergoing cardiac surgery) will aim to “de-frail” the high-risk elderly patient so as to improve their post- cardiac surgical outcomes, engage patients in active health self-management and provide knowledge translation for the implantation of best practices for this patient population (See *Figure 1*, *Table 1*, *Table 2*, *Table 3*).

2.4 The PREHAB Study – Primary Research Questions/Hypotheses

The primary research question(s) for the *Prehab* study include:

- i. What is the effect of a preoperative cardiac pre-habilitation (“*Prehab*”) program on the proportion of patients with hospital length of stay (*LOS*) > 7 days.
We hypothesize that the performance of a multifaceted, interdisciplinary cardiac “*Prehab*” program in patients awaiting an elective cardiac surgery will reduce the proportion of frail elderly patients requiring a postoperative hospital *LOS* > 7 days.
- ii. What is the effect of a preoperative cardiac pre-habilitation program in high-risk frail elderly patients on (1) pre-operative frailty, (2) exercise capacity, (3) self-managed physical activity behavior, (4) in-hospital outcomes, (5) 3-month clinical outcomes, and (6) 3 month health-related quality of life.
We hypothesize that the “*Prehab*” program for frail elderly patients awaiting an elective cardiac surgery will reduce frailty, improve exercise capacity, improve self-managed physical activity behavior, improve in-hospital outcomes, improve clinical outcomes 3 months and 1 year postoperatively, and improve health-related quality of life.

3 Study Design

3.1 Methodological Approach

The *Prehab* comprehensive inter-disciplinary program is intended to intervene to decrease frailty in high-risk elderly patients undergoing cardiac surgery.

Knowledge Gap – Will *Prehab* work in the frail, elderly?

Cardiovascular prevention and rehabilitation is a well-established and proven standard of care to decrease morbidity and mortality in patients with established and unrepaired cardiac disease.(4)(5)(6)(7)(8) In a landmark study by Arthur et al, 249 low-risk patients awaiting elective *CABG* were randomized either to an eight-week preoperative cardiac pre-habilitation (*Prehab*) program or to the usual care.(22) *Prehab* patients completed 2 exercise sessions per week and attended education classes on risk factor modification. These patients experienced shorter intensive care unit (*ICU*) and hospital lengths of stay (*LOS*) post-operatively and an improved quality of life compared to the controls, which persisted for 6 months following surgery. However, while this seminal study demonstrated the potential benefits of a “*Prehab*” program, this study was performed in younger, lower-risk patients and therefore did not address the needs of the frail, elderly patients currently being referred for cardiac surgery.

3.1.1 Preliminary Data Informing Study Methodology

The following two groundwork investigations have informed the safety and efficacy of the *Prehab* intervention and the design of the proposed phase II, randomized trial – the *Prehab* Study. We believe that the *Prehab* intervention will be able to “de-frail” high-risk elderly patients preoperatively

“The PREHAB Study” (Pre-operative Rehabilitation for reduction of Hospitalization After coronary Bypass and valvular surgery.)

and will lead to sustainable motivational changes to engage in long-term healthy living following their cardiac procedure. The implications are that this will be ultimately transferable to percutaneous cardiac intervention and other non-cardiac surgery procedures in the frail elderly.

3.1.1.1 Frailty in the Cardiac Surgery Population at St. Boniface Hospital

We undertook a systematic review of frailty in the elderly undergoing cardiac surgery (see *Table 2 & Table 3*).(23)(24)(25)(26)(27)(28)(29)(30)(31) This review demonstrated an association with increased frailty and a major negative outcomes ranging from increased institutional care to major adverse cardiac and cerebral event (*MACCE*) and increased in-hospital and long-term mortality after cardiac surgery. However, the lack of a standardized and comprehensive definition of frailty in these studies prevents clarity in understanding the interaction of frailty in the elderly and cardiac surgery. We subsequently completed a prospective examination of frailty in 133 consecutively consenting elderly cardiac surgery patients with high-levels of co-morbid disease (See *Table 4*, *Table 5*, *Table 6* and *Figure 2*). Two definitions of frailty were used (see *Appendix I*): (1) *Modified Fried criteria*: (32)(33)(34) a patient was deemed “frail” if they met ≥ 3 of the following 7 criteria: slowness (5m gait speed)(35), weakness (handgrip strength measurement)(36) and questionnaires assessing self-reported weight loss, exhaustion (the two-item Center for Epidemiologic Studies Depression (*CES-D Scale*), depression (the 5-point geriatric depression scale (*5-GDS*))(37)(38)), low physical activity (the Paffenbarger Physical Activity Index(39)(40)(41)(42)), and cognitive impairment (the Montreal Cognitive Assessment (*MoCA*))(43)(44)(45)). (2) *Short Physical Performance Battery (SPPB)*: a patient was deemed “frail” if his/her composite score was ≤ 9 based on 5m gait speed, balance tests, and the repeated chair stand test (each scored from 0 to 4)(46). Using the modified Fried or the SPPB criteria, 72 (54.1%) or 69 (51.9%) (respectively), patients studied were deemed frail (See *Table 3*). Frail patients were older, more commonly female, had higher *EuroSCORE II* values (a cardiac surgery specific mortality risk prediction score) and lower self-health ratings. Diabetes, cerebrovascular disease (*CVD*), chronic obstructive pulmonary disease (*COPD*), arthritis, anemia, peripheral vascular disease (*PVD*), and lower serum albumin were also significantly associated with being frail. Notably, frailty correlated with clinically important measures of increased hospital *LOS*: total adjusted hospital *LOS* (median 6 days (IQR: 5 – 9) in non-frail vs. 8 days (IQR 6 – 12) in “frail” patients, $p < 0.001$) and a greater proportion of patients in hospital > 7 days (37.7% in non-frail vs. 58.3% in frail patients, $p < 0.02$; See *Table 4 & Table 5*). This longer hospital stay amongst frail patients has implications for increased healthcare costs and we have observed an association between new and persistent mood disorders and reduced engagement in postoperative physical activity with a hospital *LOS* > 7 days after cardiac surgery.

3.1.1.2 A Pilot RCT of a Pre-habilitation program

We have completed a pilot, randomized control trial (manuscript proof in appendix), to demonstrate the safety and feasibility of a *Prehab* program for elective coronary artery bypass graft (*CABG*) patients. The primary outcome was walking distance based on a 6-minute walk test (*6MWT*). Secondary outcomes included 5m gait speed (23) and cardiac rehabilitation (*CR*) attendance Postop.

Improving Patient Outcomes

Fourteen patients (*StandC*, $n=7$; *Prehab*, $n=7$) completed the study (77% and 88% completion rate, respectively). None of the *Prehab* patients developed cardiac symptoms during study participation. Walking distance and gait speed remained unchanged in the Standard care group. Conversely, patients in the *Prehab* group increased their walking distance by +132 and +145 meters and gait speed improved in all seven *Prehab* group participants by 27% and 33% at Pre-op and Post-op, respectively ($p < 0.05$).

Engaging and Empowering Patients:

“The PREHAB Study” (Pre-operative Rehabilitation for reduction of Hospitalization After coronary Bypass and valvular surgery.)

A notable finding of our pilot study was the sustainability of patient self-management, as supported by a higher post-operative cardiac rehabilitation (*CR*) enrollment amongst *Prehab* (100%) than *StandC* (43%) participants.

3.2 Study Design, Setting, Population

Prehab will be a five centre prospective, randomized, open, blinded endpoint (*PROBE*) (47) controlled trial using assessor blinding and intention-to-treat analysis. The study will be conducted at four academic, tertiary care hospitals (St. Boniface Hospital, Winnipeg, MB, Queen Elizabeth II Health Sciences Centre, Halifax, NS, Montreal Heart Institute, Montreal, QC, Quebec heart and lung institute, Saint-Foy, QC) and one non-academic hospital (Saint John Regional Health Centre, Saint John, NB) that perform cardiac surgery. These sites were chosen based on similar patient populations and surgical waitlist times (48)(49). Additionally, each of these sites are partnered with one or more community-based cardiac rehabilitation (*CR*) centres, which are certified medical fitness facilities dedicated to improving the health of the community through health promotion, disease prevention and rehabilitation services. These facilities offer expert guidance from certified professionals, innovative health enhancement programs, and provide integrated medical, rehabilitative and fitness services.

3.3 Eligibility Criteria

3.3.1 Inclusion Criteria (all need to be fulfilled for eligibility)

- 1) Patients, aged 60 years or older, undergoing elective isolated coronary artery bypass grafting (*CABG*), aortic valve repair/replacement for moderate aortic stenosis or severe regurgitation, mitral valve repair/replacement for moderate stenosis or severe regurgitation or combined *CABG*/valve procedures.
- 2) Patients with Clinical Frailty Score (*CFS*) ≥ 3 (managing well) and < 7 (8 = very severely frail, approaching end-of-life or 9 = terminally ill) at time of acceptance for cardiac surgery.
- 3) Patients with an estimated ≥ 4 week wait time.

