3.4.2 Frailty Assessments

Our strategy for rapid screening of frailty in a large volume of clinic patients will be to use the 9-point Clinical Frailty Scale (*CFS*) (56)(See *Figure 4* and appendix). The *CFS* is the simplest tool to implement at multiple centres, has a high inter-observer reliability and shows good performance (by *ROC analysis*) for risk of death or institutionalization. Due to the need to screen a large number of individuals (785 patients; *Figure 5*) the use of the *Modified* and *SPPB* are less practical to implement as routine practice in the outpatient clinic sites. Therefore our approach is to use a *CFS* score of ≥ 3 as the initial indication of frailty (57) . This approach will allow us to estimate degrees of frailty in a large volume of patients in a rapid, cost-effective and highly feasible manner. All enrolled patients will be further assessed using the modified Fried criteria(33)(32)(34), and a reduction of frailty will be defined as a binary value (i.e. frail/non-frail) using these criteria(33)(32)(34).

The *SPPB* criteria will be used as a third measure.(46) As a fourth measure, our data collection protocol will also enable a Frailty Index (*FI*) calculation.(29)(56)(58)(30) The inclusion of the more definitive frailty evaluations are intended to gain more information about the different domains of frailty in the elderly to further improve the clinical frailty assessments that will be used in the future. To ensure reliability of this approach, we have compared the three measures of frailty (*CFS*, *Modified* and *SPPB*) on 169 elective cardiac surgery patients at the St. Boniface Hospital. The spearman correlation was ~ 0.65 for all three comparisons and the Cohen’s Kappa, which is a concordance measure between the different frailty definitions is ~ 0.50 . These values indicate a moderately strong link between all three measures; however it is possible that they capture somewhat different domains of frailty.

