3.5 Study Protocol

3.5.1 Screening implementation Plan

Following training, clinicians will complete a *CFS* score for every new cardiac surgery consult at each of the participating sites. Patients with a *CFS* ≥ 3 will be eligible for enrolment and notification will be sent to the site coordinator. Patients who are eligible for the study (*CFS* ≥ 3) will either be consented in person or via telephone consent process. Patients with a *CFS* ≥ 3 that either refuse to be randomized or are deemed “unsafe” will be given the opportunity to enroll in a follow up registry.

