5.2 Statistical/Analytical Plan

Objective 1: To determine if *Prehab* reduces the proportion of frail elderly patients requiring a prolonged hospital length of stay of >7 days. A univariable analysis will be undertaken to determine if hospital *LOS* > 7 days is associated with frailty and other patient-level factors. A stepwise multivariable logistic regression model will then be developed to determine if *Prehab* attendance is independently associated with a decreased risk of prolonged hospital length of stay > 7 days. As a secondary analysis, hospital *LOS* will also be compared as a continuous variable between the *Prehab* and standard care groups using a Mann-Whitney test.

“The PREHAB Study” (Pre-operative Rehabilitation for reduction of Hospitalization After coronary Bypass and valvular surgery.)

Objective 2: Does attending *Prehab* influence frailty, exercise capacity, physical activity behavior, in-hospital complications, and *HRQoL*? Although we will employ four different measures of frailty, based on our preliminary data and based on a Task Force’s position statement(90), the Modified Fried Criteria will be the primary frailty outcome over time from baseline to the end of *Prehab* program (pre-operatively), or from baseline to the 3-month post-operative follow-up. The primary measure of exercise capacity will be the *6MWT* and will be analysed with univariable linear regression models to evaluate the association between the *6MWT* and *Prehab* attendance. Accelerometers will be used to objectively measure the number of minutes spent performing moderate to vigorous physical activity (*MVPA*) and total physical activity (*TPA*) per day for a period of 7 days and compared between groups. A composite outcome for a major adverse cardiac event (i.e. *MACCE* = in-hospital stroke, myocardial infarction, renal failure requiring dialysis and death) and delirium will be compared between groups using a Chi-Square or Fisher’s Exact test. A multivariable logistic regression will be used to identify if *Prehab* is independently associated with in-hospital delirium. The *SF-12v2* and *EQ-5D* scores, after normative standardization, will be analyzed through use of a repeated *ANOVA* to allow for a standardized group and group/time interaction effect estimation.

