5.3 Sample Size Calculation

The sample size calculation was based on the primary objective – determining the effect of *Prehab* on rates of prolonged hospital length of stay > 7 days. Our preliminary data, demonstrated the proportion of frail patients in the Control group with a hospital length of stay > 7 days to be 58.3%. For the *Prehab* group, based on improvements in functional capacity in our pilot *RCT* and the work by Arthur et al14, we believe an absolute 20% reduction in proportion of patients that require prolonged hospital length of stay of greater than 7 days, is feasible. A sample size of 194 individuals (97 in each group) will be required for a two-tailed test at an alpha of 0.05 and power of 80%. All patients assigned to the pilot *Prehab* group completed the intervention, however, we are mindful that we will be recruiting frail, elderly patients who may have a higher dropout rate. Hence, we are estimating a 20% dropout rate and plan to recruit 244 individuals (122 in each study arm) to achieve an eventual sample size of 194 after dropout.

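### The randomized population (CFS 3 to 6) is broader than the frail population in the question, and the analysis plan has no step that shows whether the pooled result applies to Fried-frail patients

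*Combined protocol and SAP*

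**What the plan says.** **Entry.** Section 3.3.1 admits CFS "≥ 3 (managing well) and < 7 (8 = very severely frail, approaching end-of-life or 9 = terminally ill"). The number limits entry to levels 3 to 6. The note in brackets describes levels 8 and 9 and says nothing about level 7.

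**Status of the cut-off.** Section 3.4.2 uses a CFS "score of ≥ 3 as the initial indication of frailty". It justifies this by the need to screen many patients quickly at several centres. It then adds: "All enrolled patients will be further assessed using the modified Fried criteria". Section 3.5.2 collects frailty scores at baseline and randomizes after baseline data are complete. No section makes Fried status a condition of randomization.

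**Question.** Objective 1 in 5.2 asks whether Prehab "reduces the proportion of frail elderly patients requiring a prolonged hospital length of stay of >7 days". The hypothesis in 2.4 names the same population.

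**Sample size.** Section 5.3 takes from preliminary data "the proportion of frail patients in the Control group with a hospital length of stay > 7 days to be 58.3" per cent.

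**Analysis.** Section 5.2 examines frailty and other patient factors one at a time against LOS > 7 days, then builds a stepwise logistic model. It names no forced covariate, no estimate in frail patients and no arm-by-frailty term.

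**Screening.** Section 3.5.1 says that patients with a CFS "≥ 3 will be eligible for enrolment and notification will be sent to the site coordinator", with no upper limit.

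**The concern.** Three descriptions of the population do not coincide: the frail elderly of the question, the CFS 3 to 6 patients who are randomized, and the Fried-frail patients who supply the design rate. A patient at CFS 3 who meets fewer than three Fried criteria can be randomized and counted under an objective about frail patients.

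This matters because section 3.1 gives the reason for the trial as not knowing whether Prehab works in frail elderly patients, the earlier trial having been in younger, lower-risk ones. A positive pooled result could come largely from non-frail patients, and a null one could reflect their presence. Fried status also predicts the primary outcome strongly. Leaving it to stepwise selection means that a main prognostic variable may or may not be in the primary model, and nothing planned separates the arm effect by frailty.

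**Working it through.** **Inputs**
- From 5.3: control rate 58.3%, absolute reduction 20 points, two-sided alpha 0.05, power 80%, 97 per arm, 20% dropout, 244 recruited.
- From Table 6 (modified Fried definition): LOS > 7 days in 42/72 frail and 23/61 non-frail patients.
- From 3.1.1.1: Fried-frail share of the preliminary cohort 72/133 = 54.1%. That cohort was not selected by CFS.
- From 3.4.2: kappa of about 0.50 between frailty definitions in 169 patients. The CFS cut-off used is not stated.
- Not given: the CFS distribution, or the Fried-frail share *f* among enrolled patients. All values of *f* below are assumptions.

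**1. The plan's own figure.** Two-proportion formula, pooled variance under the null, no continuity correction:

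n = [1.96·√(2·0.483·0.517) + 0.8416·√(0.583·0.417 + 0.383·0.617)]² / 0.20² = (1.385 + 0.583)² / 0.04 = 96.8, so 97 per arm.

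Dropout: 97/0.8 = 121.25, so 122 per arm and 244 in total. The stated figures reproduce exactly.

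**2. Source of the control rate.** 42/72 = 58.3% is the Fried-frail rate. The non-frail rate is 23/61 = 37.7%. The odds ratio is (42·38)/(23·30) = 2.31.

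**3. Control rate in a mixed population.** Rate = 0.377 + 0.206·*f*.
- *f* = 0.54: 48.8% (the pooled cohort gives 65/133 = 48.9%)
- *f* = 0.75: 53.2%
- *f* = 0.90: 56.2%

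**4. Power at 97 per arm under three patterns of benefit.** The constant relative risk is 38.3/58.3 = 0.657. With benefit in frail patients only, the average effect is 20·*f* points.

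| *f* | Control rate | Same 20 points in all | Same relative risk in all | 20 points in frail only |
|---|---|---|---|---|
| 1.00 | 58.3% | 80.1% | 80.1% | 80.1% |
| 0.90 | 56.2% | 80.3% | 77.3% | 71.2% |
| 0.75 | 53.2% | 80.8% | 72.8% | 55.5% |
| 0.54 | 48.8% | 82.1% | 66.4% | 32.8% |

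**5. Where *f* might lie.** Suppose that the kappa of 0.50 applies at CFS ≥ 3, that Fried prevalence is 54.1%, and that 40% to 77% of patients score CFS ≥ 3. Then *f* is about 86% to 70%. At 40%, chance agreement is 0.492, observed agreement is 0.492 + 0.5·0.508 = 0.746, and disagreement is 0.254. The share that is CFS-positive but not Fried-frail is (0.254 + 0.400 − 0.541)/2 = 0.056, so *f* = (0.400 − 0.056)/0.400 = 0.86. This is an illustration only, since the documents give neither the margins nor the cut-off behind the kappa.

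**6. What the planned analysis can show.** Every route in 5.2 for the primary outcome gives one pooled arm effect. None gives the effect by Fried status, although the variable is available before randomization.

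**The case against.** The strongest reply is that 3.4.2 openly adopts CFS ≥ 3 as the working indication of frailty, cites a source, gives practical reasons, and discloses that agreement between scales is only moderate. Level 3 is one of four admitted levels. The randomized comparison is valid whatever the population is called. Screening by CFS should raise the Fried-frail share above the 54.1% of an unscreened cohort, so 54% is a pessimistic value. Confining benefit to frail patients is also an assumption: the cited earlier trial reported shorter stays in low-risk patients, and the pilot's walking gains were in patients not selected for frailty.

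Much of this stands, and it rules out two stronger readings. A reader might infer that the result cannot be read as an effect in frail patients at all. The documents do not support that: frailty by CFS is a declared definition, and an estimate in Fried-frail patients can be obtained from data already collected. What is missing is its pre-specification. A reader might also infer that the trial is underpowered. That depends on an unknown share and an unstated pattern of benefit, and under a uniform 20-point effect no power is lost.

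A third tempting reading is that 3.5.1 admits patients above the upper CFS limit. Section 3.3.1 requires all inclusion criteria to be met, 3.5.1 describes notification rather than randomization, and 3.5.2 has a medical director confirm eligibility. The missing limit is a wording conflict. Followed literally, it would make the sample frailer, so it does not bear on dilution.

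The reply leaves two gaps. The design rate and the entry rule still describe different populations, and the primary analysis still treats a strongly prognostic baseline variable as optional.

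**Conclusion.** The point holds in limited form. The randomized population is broader than the one in 2.4 and Objective 1, and differs from the Fried-frail group behind the 58.3%. Section 5.2 would not show whether the pooled result applies to Fried-frail patients.

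The firm evidence on size is the prognostic gap of 37.7% against 58.3% (odds ratio 2.31). The consequence for the trial is conditional. Over assumed Fried-frail shares of 54% to 90%, the expected control rate is 48.8% to 56.2%. Power at 97 per arm is 80% to 82% with a uniform 20-point effect, 66% to 77% with a constant relative risk, and 33% to 71% with benefit in frail patients only. The documents do not say which share or pattern applies. The sample-size arithmetic is correct for its stated inputs. This is a change that should be made, and it does not threaten the validity of the comparison between arms.

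**What to change.** 1. **Section 5.2.** Include baseline modified Fried status (frail/non-frail) as a fixed covariate in the primary model of LOS > 7 days by randomized arm, outside any stepwise selection. Pre-specify as supportive the arm effect in Fried-frail and in non-frail patients, with confidence intervals and an arm-by-Fried interaction term. Keep the primary test in all randomized patients.

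2. **Sections 2.4, 5.2, 5.3 and the conclusions.** Describe the randomized population by its CFS entry band. State in 5.3 that 58.3% is a Fried-frail rate, and show the control rate over an assumed Fried-frail share, for example 48.8% at 54% and 53.2% at 75%.

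3. **Separate wording point.** Reconcile the CFS limits in 3.3.1 and 3.5.1, and make the note in 3.3.1 say where level 7 falls.

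**Cost.** Protocol and SAP wording, one covariate and one interaction term, from data already collected. The subgroup estimates will be imprecise. With 54% to 75% of 97 per arm (about 52 to 73), power for 58.3% against 38.3% within the Fried-frail group is about 53% to 68%, and the interaction test will be weaker still. For that reason the subgroup results should support the main result, and claims should not rest on the Fried-frail subgroup alone.
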